REPORTING AND RESPONSE DEFINITION: Results will be presented as previously reported as the mean (+/- standard deviation) number of spot-forming-units (sfu) per 10^6 cells (frequency), calculated by subtracting the mean number of spots obtained from the no antigen control wells from the mean number obtained in the experimental wells, normalized to 10^6 starting PBMC, from 8-well replicate assays [31]. Comparison of experimental wells with control, no antigen, wells will be performed using a two-sample t-test, with $p < 0.05$ (two-sided) defined as a significant antigen-specific T-cell response. A significant antigen-specific response resulting from immunization will then be defined as a PAP-specific response detectable at the 6-month post-treatment time point (or other post-treatment time point evaluated) that is significantly higher than to media only (as above), at least 3-fold higher than the mean baseline value, and with a frequency > 10 per 10^6 PBMC.

B.2. Assessment of PAP-specific memory T-cell immunity

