1. To determine whether either treatment sequence, or PAP-specific immune response, is associated with prolonged (6-month) radiographic progression-free survival
2. To evaluate effects of schedule (concurrent versus delayed administration of pembrolizumab) on the magnitude of PAP-specific T-cell responses, PD-1 expression on circulating T cells, and PD-L1 expression on circulating epithelial cells (CEC) and on tumor biopsies
3. To determine the median time to radiographic progression using concurrent administration schedules

The exploratory objectives are to:

1. To evaluate effects of treatment on the number of circulating tumor cells
2. To evaluate PAP-specific antibody responses following treatment with pembrolizumab and pTVG-HP DNA vaccine
3. To determine whether treatment with either sequence elicits immunologic antigen spread to other prostate associated antigens

4. To determine whether pre-existing or vaccine-induced PD-L1 expression on CEC or tumor biopsies is predictive of objective clinical response
5. To determine whether treatment elicits expression of other regulatory molecules on tumor-specific T cells (e.g. TIM3, BTLA, and LAG3) or tumor cells (e.g. HVEM, phosphatidyl serine, PD-L2)
6. To determine whether PD-1-regulated antigen-specific T-cells identified by *trans vivo* DTH testing can identify patients who develop objective clinical responses with PD-1 blockade therapy in combination with pTVG-HP.
7. To determine whether changes in lymph nodes and soft tissue lesions are observed by FLT PET/CT after treatment with vaccine with or without pembrolizumab
8. To determine if PD-1 inhibitor therapy in combination with pTVG-HP will change number and activity (SUV) in osteoblastic metastases as measured by NaF PET/CT.

C. Study Design

The study is designed as a randomized, two-arm, open-label, single institution pilot trial. Study arms will be defined as follows:

- Arm 1: pTVG-HP (100 µg) with rhGM-CSF (208 µg) administered intradermally (i.d.) biweekly 6 times beginning at day 1 pembrolizumab 2 mg/kg, administered intravenously every 3 weeks 4 times, beginning at day 1
- Arm 2: pTVG-HP (100 µg) with rhGM-CSF (208 µg) administered intradermally (i.d.) biweekly 6 times beginning at day 1 pembrolizumab 2 mg/kg, administered intravenously biweekly 6 times, the first dose administered two weeks after the last pTVG-HP vaccination

Eligible subjects will be randomly assigned in 1:1 fashion to either Arm 1 or Arm 2.

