This section outlines the statistical analysis strategy and procedures for the study. Prior to the analysis of the final study data, a detailed Statistical Analysis Plan (SAP) will be written describing all analyses that will be performed.

Summary tabulations will be presented that will display the number of observations, mean, standard deviation, median, range, minimum, and maximum for continuous variables and the number and percent per category for ordinal and categorical data. All endpoints of this study will

be presented graphically where possible using boxplots and histograms for continuous variables and (stacked) bar charts for categorical variables. Data analysis will be performed using SAS[®] (SAS Institute Inc., Cary, North Carolina) version 9.3 or greater.

There are many comparisons made between the two trial arms for multiple measurements, both clinical and laboratory. However, since this a pilot study, no adjustment will be made for multiple comparisons. A two-sided test at a significance level of 0.05 will be used for all comparisons, unless noted otherwise.

F.2. Analysis Populations

The ITT population consists of all patients who are randomized. The per-protocol population consists of all evaluable patients, i.e., patients who have been treated according to protocol (all inclusion/exclusion criteria are satisfied, and adequate treatment compliance (complete treatment to at least day 43). The safety population consists of all subjects who received at least one dose of pTVG HP alone or in combination with pembrolizumab. All primary, secondary and correlative outcomes will be analyzed for both the IIT and per-protocol population. The IIT population will be the primary analysis population. Safety will be evaluated using the safety population.

F.3. Baseline Comparability

All measurements (variables) collected at baseline will be summarized and compared between study arms. These include demographic variables, ECOG PS, lab parameters (CBC, chemistry panel, serum testosterone, PSA and PAP) medical history information and CTCs. Comparisons between study arms of baseline variables on a continuous scale will be performed using a two-sample t-test and/or nonparametric Wilcoxon Rank Sum test. Comparisons between study arms of baseline variables on a categorical scale will be performed using Fisher's exact test.

F.4. Analysis of Primary Endpoints

F.4.1. Analysis of Toxicity Rates and Serum Chemistry Parameters

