F.4.3. Objective Response Rate and PSA Response Rate

The objective response rate and PSA response rate will be calculated for each study arm and for both arms combined along with the corresponding 95% confidence intervals. The Wilson score method will be used to construct the confidence intervals. Fisher's exact test will be used to compare the objective response and PSA response rates between study arms. Duration of response will be analyzed using the Kaplan-Meier method.

F.5. Analysis of Secondary Endpoints

F.5.1. PAP-Specific Immune Response

The number and frequencies of PAP-specific immune responses will be summarized in tabular format for each study arm and both study arms combined. A log-linear model will be used to evaluate whether PAP-specific immune response predicts the 6-months progression-free survival rate. The interaction between treatment (pembrolizumab administered sequentially versus delayed) and PAP-specific immune response will be included in the model. Analogously, a Cox proportional hazard regression model will be used to examine the association between PAP-specific immune response and the time to radiographic progression.

F.5.2. PAP-Specific T-Cell Response, PD-1 Expression, PD-L1 Expression

PD-1 and PD-L1 expression levels will be summarized in terms of means, standard deviations and ranges for each study arm separately and for both arms combined. The number and frequencies of PAP-specific T-cell responses will be summarized in tabular format. Fisher's exact test will be used to compare the PAP-specific T-cell response rates between study arms. A linear regression model or a negative binomial regression model will be utilized to evaluate the effects of schedule (concurrent versus delayed administration of pembrolizumab) on PD-1 expression on the number of circulating T cells, and PD-L1 expression on the number of circulating epithelial cells. The

choice of the model will be dependent on the distribution of the outcome variables (number of circulating T-cells and number of circulating epithelial cells).

F.6. Exploratory Analyses

F.6.1. Evaluation of Treatment Effects on the Number of Circulating Tumor Cells

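### Secondary objective 2 asks whether schedule changes the magnitude of PAP-specific T-cell responses, but the only between-arm test planned for these responses compares yes/no response rates

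*Combined protocol and SAP*

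**What the plan says.** Sections 3.B and 11.B give the second secondary objective as "To evaluate effects of schedule (concurrent versus delayed administration of pembrolizumab) on the magnitude of PAP-specific T-cell responses", followed by PD-1 and PD-L1 expression. The summary in Section 2.F likewise says that the trial will look at whether sequencing affects the size of the immune response.

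The matching analysis is Section 11.F.5.2. It tabulates numbers and frequencies of PAP-specific T-cell responses and then names Fisher's exact test, which "will be used to compare the PAP-specific T-cell response rates between study arms". The same section adds a model: "A linear regression model or a negative binomial regression model will be utilized to evaluate the effects of schedule". That sentence goes on to PD-1 and PD-L1 expression, and its outcomes are counts of circulating T cells and circulating epithelial cells. PAP-specific T-cell frequency is not among them.

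Sections 10.B.1 to 10.B.3 define the readouts. ELISPOT, proliferation and intracellular cytokine staining each give a mean and standard deviation of a frequency. An ELISPOT responder must be significantly above medium alone and "at least 3-fold higher than the mean baseline value, and with a frequency > 10 per 10^6 PBMC". The other two assays use the same structure with a cut-off of 100 per 10^6 CD4+ or CD8+ T cells. Section 10.B sets the primary immune analysis at 6 months against pre-treatment. Section 11.F.1 gives the default test: "A two-sided test at a significance level of 0.05 will be used for all comparisons, unless noted otherwise".

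**The concern.** The objective is about how large the response is, while the test is about how many patients cross a threshold. Two schedules could differ several-fold in T-cell frequency and show similar responder rates. The reverse is also possible.

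The gap is uneven within the plan. Exploratory circulating tumour cell counts (11.F.6.1) get between-arm tests of level and of change, plus mixed models. Exploratory FLT SUV values (11.F.6.7) get a log transformation and a between-arm test of change. The secondary objective that names magnitude gets neither.

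At stake is whether the trial can say anything inferential about schedule and the size of the T-cell response. The question matters to the programme: Section 2.F cites a lower frequency of immune response in Arm 3 among the reasons for opening Arm 4. A test on dichotomised data in arms this small is also usually weaker and more conservative than one on the measured values.

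**Working it through.** **Objective against analysis.** The mismatch needs no arithmetic. Objective: magnitude, by schedule. Between-arm test in 11.F.5.2: response rates. Regression in 11.F.5.2: PD-1 and PD-L1 only. No other between-arm test of PAP-specific T-cell frequency appears in Section 11.F.

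**Inputs from the documents.** At least 12 evaluable patients per arm before Arms 1 and 2 close (2.F, 6.A); 15 planned and 16 randomised per arm (11.E); two-sided 0.05 (11.F.1). The documents give no SD, effect size, baseline level, responder rate or power for this comparison.

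**The plan's own power figure.** Section 11.E is about 6-month progression-free survival, not T cells. Exact enumeration of Fisher's test with 15 per arm at one-sided 0.10 gives 82.3% power for 25% vs 70% and 82.7% for 20% vs 65%. The stated 80% reproduces.

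**Cost of the yes/no cut, unadjusted.** Assume that log frequency is normal with equal SD, that schedule shifts it by d SD, and that a threshold defines response. Worked case: 15 per arm, comparator response rate 20%, d = 1.
- Threshold: z = 0.84. Response rate in the other arm: 1 − Φ(0.84 − 1) = 56%.
- Fisher, 56% vs 20%, by exact enumeration: 36.6% power.
- t-test on the measured values: noncentrality d·√(n/2) = √7.5 = 2.74 on 28 df, 75.3% power.
- Loss: 75.3 − 36.6 = 38.7 points.

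Over comparator response rates of 10% to 50% with 15 per arm, the t-test has 75% and Fisher 30–39% at d = 1 (loss 36–45 points). At d = 0.5 they have 26% and 5–9% (loss 17–21).

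**Cost against a baseline-adjusted model.** Assumptions: log10 SD 0.6, so 1 SD is a 10^0.6 ≈ 4-fold difference; baseline-to-post correlation 0.3–0.7; baseline median 10 per 10^6; comparator rise 2-fold; responder = at least 3 times baseline and above 10 per 10^6. The additional requirement of significance against medium was not simulated.

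| Per arm | Shift | Fisher | ANCOVA on log frequency |
|---|---|---|---|
| 12 | 1 SD | 29–58% | 66–89% |
| 15 | 1 SD | 33–65% | 78–95% |

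Type I error in these runs was 1.6–2.4% for Fisher and 4.4–5.4% for ANCOVA.

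**Spread over assumptions.**
- 1-SD shift: about 26–45 points. Some settings fall outside: 24 with a Wilcoxon test, 12 per arm and a 30% comparator response rate; up to 50 if the comparator post-treatment median is 10 or 40 instead of 20.
- 0.5-SD shift: about 14–33 points. Here the adjusted model itself has only 21–44% power.
- Half of comparator values at the assay floor, Wilcoxon, 15–16 per arm: 12–39 points over shifts of 0.5–1.5 SD.
- Schedule changes mainly who responds (a mixture of responders and non-responders): about 2–6 points against an unadjusted Wilcoxon test, and up to 26 against an adjusted model.

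**Two gains, not one.** At correlation 0.7 and a 1-SD shift, Fisher has 58% (12 per arm) and 66% (15 per arm), an unadjusted t-test 66% and 74%, and ANCOVA 88% and 95%. Avoiding the cut gains about 8 points (66 − 58; 74 − 66). Baseline adjustment gains the other 22 and 21 (88 − 66; 95 − 74). At correlation 0.3 the cut accounts for most of the loss.

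**The case against.** A reader might infer that the plan forfeits 26 to 45 points of power as a fixed cost. The documents do not support that. They give none of the quantities needed, and the range belongs to a roughly 4-fold difference between schedules on a log-normal scale. Section 2.D reports patients with no detectable response after 24 immunizations, so a floor or a responder mixture is at least as plausible, and there the loss can be a few points. Part of the larger figures comes from covariate adjustment, which is a separate choice. This objection stands, and it limits the size of the claim.

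A reader might also infer that magnitude is ignored altogether, or that baseline is unused. Neither is right. Sections 10.B.1 to 10.B.3 report mean frequencies, 11.F.1 plans summaries and plots of continuous variables, and the 3-fold rule uses each patient's own baseline. What is missing is a between-arm test of magnitude and the use of baseline as a covariate.

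Finally, this is one unpowered secondary comparison in a pilot trial without multiplicity control. Section 11.F.1 promises a detailed SAP, and regression for schedule effects already appears in 11.F.5.2, so the gap may be a drafting slip. That tempers its weight but does not fill the gap: as written, following the plan leaves the objective untested.

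**Conclusion.** The point holds as a mismatch between objective and analysis. Secondary objective 2 concerns magnitude, and the only between-arm test specified for PAP-specific T-cell responses is Fisher's test on yes/no rates.

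The power consequence is illustrative and conditional. With 12 to 16 per arm at two-sided 0.05, the loss is about 26–45 points for a 1-SD shift in log10 frequency, about 14–33 for 0.5 SD, and about 2–26 if schedule mainly changes who responds. Fisher's actual type I error is about 2% under the shift assumptions simulated. All of these rest on an assumed SD, baseline level, correlation and responder rate. The primary endpoints are not affected. It should be corrected before the final analysis because the correction is cheap.

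**What to change.** Add to 11.F.5.2, and carry into the detailed SAP, a between-arm comparison (Arm 1 vs Arm 2) of PAP-specific T-cell frequency at 6 months that uses the pre-treatment value. State which assay readouts it covers.

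The method must tolerate zero and negative values. Section 10.B.1 subtracts the no-antigen wells and scales from 10^5 cells per well to 10^6, a factor of 10. A mean only 0.1 spot per well below background therefore gives −1 per 10^6, and log(−1 + 1) is undefined. A negative binomial model cannot take negative subtracted values either. Suitable choices are:
- a rank-based ANCOVA;
- a Wilcoxon rank-sum test on change from baseline;
- ANCOVA on the log scale with a pre-stated floor for values at or below background.

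Keep Fisher's exact test on responder rates as supportive. The cost is SAP wording and a little more analysis; no new data are needed.

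### The schedule regression in 11.F.5.2 takes cell numbers as its outcomes, so it does not isolate the PD-1 and PD-L1 expression that secondary objective 2 asks about

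*Combined protocol and SAP*

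**What the plan says.** Secondary objective 2 appears in the synopsis, Section 3.B and Section 11.B. It has two parts. The first is the "effects of schedule (concurrent versus delayed administration of pembrolizumab) on the magnitude of PAP-specific T-cell responses". The second is the effect of schedule on "PD-1 expression on circulating T cells, and PD-L1 expression on circulating epithelial cells (CEC) and on tumor biopsies".

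Section 11.F.5.2 is the matching analysis and contains three elements:

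- **Description.** "PD-1 and PD-L1 expression levels will be summarized in terms of means, standard deviations and ranges for each study arm separately". A pooled summary is also planned.
- **PAP-specific T-cell response.** Responses are tabulated, and a Fisher's "exact test will be used to compare the PAP-specific T-cell response rates between study arms".
- **Regression.** "A linear regression model or a negative binomial regression model will be utilized to evaluate the effects of schedule", the stated target being its effect "on PD-1 expression on the number of circulating T cells, and PD-L1 expression on the number of circulating epithelial cells". The next sentence lets the distribution of the outcome variables decide between the two models, and identifies those variables as "number of circulating T-cells and number of circulating epithelial cells".

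**The concern.** The objective is about a property of the cells: whether, or how strongly, they carry PD-1 or PD-L1. The regression, as its outcomes are defined, is about how many cells there are. An analyst who follows the text could report a schedule effect when only cell number differs. The same analyst could report no effect in the model when expression differs and cell number does not. The regression is the only inferential analysis that F.5.2 offers for the PD-1 and PD-L1 part of the objective. An unclear outcome also leaves room to choose among percent positive, intensity and count after the data are seen, in an open-label trial where Section 11.F.1 applies no multiplicity adjustment.

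**Working it through.** The plan gives no figure to reproduce. The check is a comparison of sections, followed by a small illustration.

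**1. Objective against analysis**

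| Component of objective 2 | What 11.F.5.2 provides |
|---|---|
| Magnitude of PAP-specific T-cell response | Fisher test by arm, on response rates rather than magnitude |
| PD-1 on circulating T cells | Summary by arm; regression whose named outcome is T-cell number |
| PD-L1 on CEC | Summary by arm; regression whose named outcome is CEC number |
| PD-L1 on tumor biopsies | At most the general summary of PD-L1 levels; no comparison between schedules |

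**2. Does another section fill the gap?** No.

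- F.5.1 relates PAP-specific immune response to progression.
- F.6.1 compares the number of circulating tumor cells between arms.
- F.6.2 and F.6.3 cover antibody response and antigen spread.
- F.6.4 uses PD-L1 as a predictor of clinical response, with arms combined.
- F.6.5 covers other regulatory molecules.
- F.6.6 uses PD-1-regulated responses from DTH testing as a predictor of response.
- F.6.7 and F.6.8 concern imaging.
- Section 10.D has a blinded pathologist assess change in biopsy PD-L1 from pre-treatment to week 12, but names no comparison by schedule.

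**3. What each reading of the regression would estimate.** The values are assumed, for illustration only. Two groups, A and B, have these average CEC:

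- Case 1: A has 20 CEC, 10% PD-L1-positive. B has 20 CEC, 60% positive.
- Case 2: A has 20 CEC, 30% positive. B has 40 CEC, 30% positive.

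| Ratio B to A | Case 1 (expression differs) | Case 2 (only number differs) |
|---|---|---|
| All cells (literal reading) | 20/20 = 1.0 | 40/20 = 2.0 |
| Positive cells (charitable reading) | (20 × 0.60)/(20 × 0.10) = 12/2 = 6.0 | (40 × 0.30)/(20 × 0.30) = 12/6 = 2.0 |
| Percent positive (the objective) | 60/10 = 6.0 | 30/30 = 1.0 |

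The literal reading is wrong in both cases. The charitable reading is right in case 1 and wrong in case 2.

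**4. Effect of an offset.** With log(expected positive cells) = log(total cells) + b0 + b1 × group, exp(b1) is the ratio of proportions. Case 1 gives (12/20)/(2/20) = 6.0 and case 2 gives (12/40)/(6/20) = 1.0. Both match the objective.

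**The case against.** The strongest reply is that this is loose wording. The heading of F.5.2 and the regression sentence both speak of expression. Numbers of PD-1-positive T cells and PD-L1-positive CEC would suit a linear or negative binomial model. Total circulating tumor cell number already has its own analysis in F.6.1, so a second bare count under an expression heading is unlikely to be intended. This is plausible, and on that reading case 1 would be detected. But the explicit outcome definition does not say it, and case 2 shows that positive counts without a denominator still confuse number with expression.

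A reader might go further and infer that F.5.2 leaves objective 2 wholly untested, or that even a large change in expression would go unseen. The documents do not support either. The T-cell component has a Fisher test, and expression levels are reported by arm, so 10% against 60% would show in the tables without a formal test. Nor is the missing baseline term an error: Arms 1 and 2 are randomized, and adjustment mainly buys precision.

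It is also fair to say that the stakes are limited. This is a secondary endpoint in a pilot with 16 patients per randomized arm, Section 10.C says its circulating tumor cell results are not strictly quantitative, and F.1 promises a detailed SAP before the final analysis. That makes correction easy, but the current text still points to the wrong quantity.

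**Conclusion.** The point holds for the regression and for the biopsy component. As written, the model analyzes cell numbers. On the more generous reading it analyzes marker-positive cell numbers. Neither isolates expression, and PD-L1 on biopsies has no between-schedule comparison. For the PD-1 and PD-L1 part of objective 2, what remains is description by arm. The size cannot be given as a number from the documents: the ratios above rest on assumed cell counts and percentages, and the actual distortion depends on how far cell number differs between arms. The conclusion itself depends only on the stated outcome definition and on no other section testing expression by schedule. Confidence is high that the text needs correcting, and lower about what was intended.

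**What to change.** In 11.F.5.2, replace the parenthetical outcome definition with expression outcomes:

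- PD-1 on circulating T cells: percent positive, or MFI.
- PD-L1 on CEC: percent positive, or PD-L1-positive count with total CEC as offset if raw counts are kept.
- PD-L1 on biopsies: the blinded pathologist's reading.

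Compare each between Arm 1 and Arm 2 at a named time point, adjusting for the pre-treatment value where available. Section 10.B already makes 6 months the primary time point for immune analysis, which is a natural choice for the blood markers. Biopsies are taken only pre-treatment and at about week 12, and in Arm 2 the second one precedes the first pembrolizumab dose. That comparison therefore sets the combination against vaccine alone and should be labelled so. Section 9 aims for at least 6 evaluable pairs per arm, so about 12 in all if the aim is just met. Present it as low-precision.

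The cost is slightly more than a wording change. Section 10.C lists CD45, EpCAM, PD-1, CTLA-4 and DAPI as a minimum panel, commits to reporting only PD-1 and CTLA-4 on these cells, and expresses cell number as a percentage of live events. PD-L1 should be added to the panel and the reporting (it was stained in the Figure 7 work that the section cites), and raw counts retained if an offset model is wanted. Sample size, power and alpha are unaffected.
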